3.3.2. Anti-RSV Prefusion F IgG

IgG levels will be determined against both RSV A and RSV B preF antigens in a direct-binding Luminex immunoassay. Refer to [Section 5.3.2](#) for LLOQs.

Titers above the LLOQ are considered accurate and their quantitated values will be reported. Titers below the corresponding LLOQ or denoted as BLQ will be set to $0.5 \times \text{LLOQ}$ for analysis. Missing assay results will not be imputed. Calculations and derivations will be based on imputed values.

In addition to IgG concentration, the anti-RSV preF IgG fold rise will be derived. These will be similar to NT ([Section 3.2.1](#)).

3.3.3. Ratio of Combined Neutralizing Titer A/B Fold Rise to Combined Anti-RSV Prefusion F IgG A/B Fold Rise

This endpoint will be derived by combining individual level assay data – NT and anti-RSV preF IgG.

- Combined NT A/B fold rise: For each individual, the combined RSV A/B–50% neutralizing fold rise is the geometric mean of the fold rise of RSV A–50% and the fold rise of RSV B–50%.

- Combined anti-RSV preF IgG A/B fold rise: For each individual, the combined RSV A/B–IgG fold rise is the geometric mean of the fold rise of RSV A–IgG and the fold rise of RSV B–IgG.
- Ratio: For each individual, the ratio is calculated using the individual combined RSV A/B–50% NT fold rise as numerator and using the individual combined RSV A/B–IgG fold rise as denominator.

This should be derived for all applicable visits with NT and IgG results.

3.3.4. Anti-RSV Nonvaccine Antigen Immunoglobulin

Four nonvaccine antigens (NVAs) will be assessed: matrix, nucleoprotein, Ga peptide, and Gb peptide. In the analysis, Ga and Gb are considered as 1 antigen, though there are 2 different assays. Refer to [Section 5.3.2](#) for LLOQs.

Titers above the LLOQ are considered accurate and their quantitated values will be reported. Titers below the corresponding LLOQ or denoted as BLQ will be set to $0.5 \times \text{LLOQ}$ for analysis. Missing assay results will not be imputed. Calculations and derivations will be based on imputed values.

The following binary variables will be derived:

1. Subjects with ≥ 4 -fold rise on matrix.
2. Subjects with ≥ 4 -fold rise on matrix and ≥ 4 -fold rise on G (either Ga or Gb).
3. Subjects with ≥ 4 -fold rise on all 3 antigens: matrix, G (either Ga or Gb), and nucleoprotein.
4. Subjects with ≥ 4 -fold rise on any of the 3 antigens.
5. Seroconversion for possible RSV infection will be defined later.

Specifically, the above variables will be derived for each cohort:

- For the Primary Stage Cohort - Stage 1, these will be derived from before Vaccination 1 to each applicable post–Vaccination 1 visit in Stage 1.
- For the Primary Stage Cohort - Stage 2, these will be derived from before Vaccination 2 to each applicable post–Vaccination 2 visit in Stage 2.
- For the RSV Vaccine Month-0, Month-2 Cohort, these will be derived from before Vaccination 2 to each applicable post–Vaccination 2 visit.

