
RSV Vaccine Month-0, Month-2 Cohort
 
To describe the safety and tolerability of the first and second dose of an adjuvanted RSV vaccine administered 2 months apart.
 
To describe the immune responses elicited by the first and second dose of adjuvanted RSV vaccine administered 2 months apart.
	
RSV Vaccine Month-0, Month-2 Cohort
 
 • Local reactions within 14 days after Vaccinations 1 and 2. • Systemic events within 14 days after Vaccinations 1 and 2. • AEs within 1 month after Vaccinations 1 and 2. • AEs from Vaccination 1 through 1 month after Vaccination 2. • Medically attended AEs and SAEs through 12 months after Vaccination 2. • RSV A– and RSV B–neutralizing antibody titers measured at scheduled timepoints before and after each vaccination scheduled. • Plasmablast frequencies and T-cell phenotype and functional analysis before each vaccination and 1 week after Vaccinations 1 and 2 (PBMC subjects). • Memory B-cell and T-cell frequencies and their functional analysis before each vaccination, and 1 and 6 months after Vaccinations 1 and 2. • IgG titers against prefusion F at scheduled timepoints before and after each vaccination. • IgG titers to nonvaccine RSV antigens at scheduled timepoints before and after each vaccination.

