3.2.1. RSV A– and RSV B–Neutralizing Antibody Titers

RSV A– and RSV B– neutralizing antibody titers will be determined on all sera collected at applicable visits for antibody testing.

Titers above the lower limit of quantitation (LLOQ) are considered accurate and their quantitated values will be reported. Refer to [Section 5.3.2](#) for LLOQs. Titers below the corresponding LLOQ or denoted as below the limit of quantitation (BLQ) will be set to $0.5 \times \text{LLOQ}$ for analysis. Missing assay results will not be imputed. Calculations and derivations will be based on imputed values.

In addition to titer, the neutralizing titer (NT) fold rise from before vaccination will be derived for both RSV A and RSV B as detailed below:

1. For the Primary Stage Cohort - Stage 1: NT fold rise will be derived from before Vaccination 1 to each post–Vaccination 1 visit with NT assay performed.
2. For the Primary Stage Cohort - Stage 2:
 - a. NT fold rise will be derived from before Vaccination 2 to each post–Vaccination 2 visit with NT assay performed.
 - b. NT fold rise will be derived from before Vaccination 1 to each post–Vaccination 1 visit (including any post–Vaccination 2 visits and at the Vaccination 2 visit) with NT assay performed.
 - c. NT fold rise will be derived from 1 month after Vaccination 1 to 1 month after Vaccination 2.

3. For the RSV Vaccine Month-0, Month-2 Cohort:
 - a. NT fold rise will be derived from before Vaccination 1 to each applicable post-Vaccination 1 visit (note: 2 months after Vaccination 1 is the same as before Vaccination 2).
 - b. NT fold rise will be derived from before Vaccination 2 to each post-Vaccination 2 visit with NT assay performed.
 - c. NT fold rise will be derived from 1 month after Vaccination 1 to 1 month after Vaccination 2.

For calculating a fold rise, $< \text{LLOQ}$ will be converted to $0.5 \times \text{LLOQ}$ for a numerator, and $< \text{LLOQ}$ will be converted to LLOQ for a denominator when only one of either the numerator or denominator is $< \text{LLOQ}$. If both the numerator and denominator are $< \text{LLOQ}$, then both will be converted in the same way.

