- Memory B-cell and T-cell frequencies and their functional analysis before each vaccination and 1 and 6 months after Vaccinations 1 and 2.
- IgG titers against preF at scheduled time points before and after each vaccination.
- IgG titers to nonvaccine RSV antigens at scheduled time points before and after each vaccination.

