6.4. Subset Analyses

Subgroup analysis for immunogenicity results (NT) may be carried out by anti-RSV NVA immunoglobulin seroconversion at certain visits or across some visits. As the definition of NVA seroconversion was to estimate possible nonsymptomatic RSV infection, stratified analyses may help to elucidate the relationship between immune response induced by RSVpreF and possible infection.

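### In the Month-0/Month-2 Cohort the nonvaccine-antigen infection variables start only before Vaccination 2, so RSV infections between the doses get no planned individual-level flag

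*SAP*

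**What the plan says.** SAP 3.3.4 lists four binary variables built on rises of at least 4-fold: matrix alone, matrix plus G, all three antigens, and "Subjects with ≥ 4 -fold rise on any of the 3 antigens". Of a fifth it says only: "Seroconversion for possible RSV infection will be defined later".

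The starting point differs by cohort:
- Stage 1: "these will be derived from before Vaccination 1 to each applicable" post-Vaccination 1 visit in that stage.
- Stage 2: from before Vaccination 2. The same subjects are already covered from Vaccination 1 by the Stage 1 rule.
- Month-0/Month-2 Cohort: "For the RSV Vaccine Month-0, Month-2 Cohort, these will be derived from before Vaccination 2 to each applicable" post-Vaccination 2 visit.

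SAP 6.3.4 tabulates only these variables. It plans no NVA geometric mean or fold-rise summary.

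For the same cohort, Protocol Section 2 lists as an endpoint "IgG titers to nonvaccine RSV antigens at scheduled timepoints before and after each vaccination", and SAP 3.3 repeats it: "IgG titers to nonvaccine RSV antigens at scheduled time points before and after each vaccination". SAP 2.2 schedules antibody sera before each dose, 1 month after the first, and 1, 6 and 12 months after the second. SAP 3.2.1 derives neutralizing titer (NT) fold rises from before Vaccination 1, noting that "2 months after Vaccination 1 is the same as before Vaccination 2", and also from before Vaccination 2.

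SAP 6.4 gives the purpose of NVA seroconversion as estimating possible nonsymptomatic infection, and says that "stratified analyses may help to elucidate the relationship between immune response induced by RSVpreF and possible infection".

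**The concern.** The Month-0/Month-2 rule has the same form as the Stage 2 rule, but this cohort has no earlier stage to cover the time after its first dose. It is the only cohort in which vaccinated subjects are followed for a period without the marker. The part of the listed NVA endpoint that concerns the first dose has no analysis.

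Three results rest on titers that an infection in this interval could alter:
- GMTs and NT fold rises after the first dose, measured from before Vaccination 1. An infection adds to these.
- The second-dose fold rise measured from before Vaccination 2. An infection raises the reference and shrinks the rise.
- The 1-month GMRs in SAP 6.2.1.2 (NT) and 6.3.3 (IgG). They compare the 240 µg CpG/Al(OH)₃ arm given with influenza vaccine in Stage 1 against the same formulation given alone in this cohort. Infections can be flagged from Vaccination 1 in the first arm but not in the second. The cohorts were not randomized against each other and enrolled at different times, so RSV exposure may differ.

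**Working it through.** **1. Visits side by side (Protocol Table 3; SAP 2.2, 3.2.1, 3.3.4).**

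| Visit (month) | Serum drawn | NT fold rise from before Vaccination 1 | NVA variable |
|---|---|---|---|
| 1 (0) | yes | reference | none |
| 2 (1) | yes | yes | none |
| 3 (2) | yes | yes | reference |
| 4 (3) | yes | yes | yes |
| 5 (8) | yes | yes | yes |
| 6 (14) | yes | yes | yes |

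The marker is derived at 3 of the 5 antibody visits after Vaccination 1. The uncovered interval is 54 to 66 days. As a share of follow-up from Vaccination 1 to the last visit (350 to 378 days after Visit 3) it runs from 54/(54+378) = 12.5% to 66/(66+350) = 15.9%.

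**2. How a flag is lost (illustrative titers).** Suppose an NVA titer rises 8-fold between Visits 1 and 3, then is flat or halved at Visit 4. Measured from Visit 1 the ratio is 8 or 4, which is flagged. Measured from Visit 3 it is 1 or 0.5, which is not. If the rise by Visit 3 is only 4-fold and then halves, the Visit 4 ratio from Visit 1 is 2. That infection is caught only if the variable is also derived at Visit 3.

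**3. Expected infections among vaccinees.** The documents give no RSV attack rate. I assume 3% to 10% per year, spread evenly, with 31 vaccinees (Protocol Table 4) and a 60-day interval.
- Whole interval: 31 × 60/365 × 0.03 = 0.15, and with 0.10 it is 0.51.
- Before the 1-month sample (28 to 35 days): 31 × 28/365 × 0.03 = 0.07, and 31 × 35/365 × 0.10 = 0.30.
- Chance of at least one over the whole interval: 1 − (1 − p)^31. As a check on the formula, Protocol Table 11 states 0.14 for p = 0.5% and n = 31; the formula gives 0.144. Here p = 0.03 × 60/365 = 0.49% up to 0.10 × 60/365 = 1.64%, giving 0.14 to 0.40.
- If the whole interval fell inside an RSV season of 105 days (midpoint of the 3 to 4 months in Protocol 1.2): 31 × 60/105 × (0.03 to 0.10) = 0.5 to 1.8.

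**4. Effect of one infected vaccinee.** With an extra NT rise of f in 1 of 31 subjects, the arm GMT is multiplied by f^(1/31). For assumed f = 4 this is 1.046; for f = 8 it is 1.069. If the infection raises only the pre-Vaccination 2 titer, the second-dose GMFR is divided by the same factors.

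**5. Against sampling error.** With 31 per arm and an assumed SD of 0.8 to 1.0 on the natural-log scale, the 95% limits of a GMR lie a factor exp(2.00 × SD × √(2/31)) either side, which is 1.50 to 1.66. A 5% to 7% shift is well inside that.

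**The case against.** The best reply is that little depends on this. The cohort is exploratory and all analyses are descriptive. It has a concurrent 1:1 placebo arm with GMTs at every visit, so infection between the doses would show as a placebo rise at Months 1 and 2. The NVA titers should exist, because Protocol 7.2.1 commits the sera to that assay. The only link from NVA status to NT results is SAP 6.4, which is optional, allows a flexible choice of visits, and waits for a definition of seroconversion.

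These points limit the size of the problem but do not remove it. The placebo arm gives group-level evidence only. It cannot identify infected vaccinees, and it does not protect the cross-cohort GMR. Titers that exist but enter no planned derivation are not an analysis.

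A reader might infer more than the documents support, in four ways:
- *That NVA is the plan's only guard against infection.* The placebo arm is another.
- *That infections between the doses always pass as vaccine response.* They inflate results from before Vaccination 1 but understate fold rises from before Vaccination 2. One shortly before Visit 3 may still be flagged if NVA titers keep rising 4-fold.
- *That a corrected derivation would correct the GMR.* No planned GMT, GMFR or GMR excludes or adjusts for NVA status, in Stage 1 or here.
- *That several infections are to be expected.* Counting all 62 subjects in full season gives up to 62 × 60/105 × 0.10 = 3.5. Only the 31 vaccinees' infections can be mistaken for vaccine response, only 28 to 35 days bear on the 1-month sample, and enrollment is stated to precede the influenza season. No dates are given, so some overlap with RSV circulation cannot be excluded.

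**Conclusion.** The point holds as a gap in a stated derivation rule. For this cohort SAP 3.3.4 does not deliver the NVA endpoint that the protocol and SAP 3.3 list, and it is out of step with the NT derivation in the same cohort and the NVA derivation in Stage 1. An infection between the doses has no planned individual flag and can suppress later ones.

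The numerical consequence is probably small: an expected 0.15 to 0.5 infected vaccinees between the doses, of which 0.07 to 0.3 precede the 1-month sample, and about 5% to 7% on the arm GMT for each one. These figures rest on an attack rate, an even spread over the year and an extra NT rise that are my assumptions. In-season values would be higher. The change is still worth making, because the marker's purpose is to identify such subjects and these analyses feed the choice of dose, formulation and schedule (SAP 7.2).

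**What to change.** In SAP 3.3.4, for the Month-0/Month-2 Cohort:
- Derive binary variables 1 to 4 from before Vaccination 1 to each later antibody visit: 1 month after Vaccination 1, before Vaccination 2, and 1, 6 and 12 months after Vaccination 2.
- Keep the existing derivation from before Vaccination 2.
- Define variable 5 before this cohort is unblinded, and apply it from both starting points. Until it is defined, the SAP 6.4 subgroups cannot be formed in any cohort.

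The cost is about one sentence plus extra columns in the SAP 6.3.4 table. No visit, sample or unplanned assay is added. The change alters the reported NVA percentages and lets the optional subgroup analysis cover the interval between the doses. It leaves every planned GMT, GMFR and GMR as it is.

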3.3.5. Cellular Assays

PBMCs isolated from whole blood will be used for evaluation of cellular immune responses to the RSV vaccine formulations. Polyfunctional CD4 and CD8 T cells will be analyzed. Exploratory analyses may also include characterization of memory B-cell, plasmablast, and T-cell immune responses, and repertoire analyses. Refer to [Section 5.3.2](#) for a list (not inclusive) of these exploratory assays.

3.4. Baseline Variables

3.4.1. Baseline Definition

Day 1 is defined as the day of Vaccination 1. Measurements or samples collected prior to Vaccination 1 on Day 1 are considered the baseline data for the assessments.

3.4.2. Demographics, Smoking History, and Medical History

Demographic variables collected include sex, race, ethnicity, and date of birth. Age at the time of vaccination (in years) will be derived based on birthday. For example, if the vaccination date is 1 day before the subject's 86th birthday, the subject is 85 years old.

Medical history of clinical significance will be collected and categorized according to the current version (at the time of reporting) of the Medical Dictionary for Regulatory Activities (MedDRA).

Subject smoking history is also collected at Visit 1.

3.4.3. E-Diary Completion

An e-diary will be considered transmitted if any data for the local reactions, systemic events, or use of antipyretic/pain medication are present for any day. If all data are missing for all items on the e-diary for all 14 days (local reactions, systemic events, and use of antipyretic/pain medication) after vaccination, then the e-diary will be considered not transmitted. An e-diary will be considered transmitted for a given day if any data are present for that day.

3.4.4. Nonstudy Vaccines

Any nonstudy vaccinations given will be recorded in the CRF from the time of signing of the informed consent document (ICD) to the 12-month follow-up visit (Visit 5 for Primary Study Cohort - Stage 1 subjects, Visit 9 for Primary Study Cohort - Stage 2 subjects, and Visit 6 for RSV Vaccine Month-0, Month-2 Cohort subjects).

Nonstudy vaccinations will be categorized according to the latest version (at the time of reporting) of the World Health Organization (WHO) Drug Dictionary.

3.5. Safety Endpoints

Refer to [Section 3.1](#) and [Section 3.3](#).

4. ANALYSIS SETS

Data for all subjects will be assessed to determine if subjects meet the criteria for inclusion in each analysis population prior to unblinding and releasing the database, and classifications will be documented per standard operating procedures.

Three analysis populations will be defined for each of the 3 study cohorts: Primary Study Cohort - Stage 1, Primary Study Cohort - Stage 2, and RSV Vaccine Month-0, Month-2 Cohort.

4.1. Primary Study Cohort - Stage 1

4.1.1. Safety Population

All subjects receiving at least 1 dose of the investigational products (respiratory syncytial virus stabilized prefusion F subunit vaccine [RSVpreF] or placebo) at Visit 1 will be included in the safety population for this cohort. For the safety analyses, subjects will be analyzed according to the investigational product received. The safety population will be the only analysis population for safety evaluation included in [Stage 1](#).

4.1.2. Evaluable Immunogenicity Population

This analysis population will include subjects who:

- Are eligible (have signed informed consent and met all inclusion/not met any exclusion criteria) and were randomized into the study;
- Have received both the SIIV and RSV vaccine or placebo and SIIV as randomized;
- Have a Visit 2 (1 month after vaccination) blood draw for assay testing within 27 to 42 days after Visit 1 (after vaccine administration) (note: the 27- to 42-day interval is calculated as the Visit 2 date minus the Visit 1 date);
- Have at least 1 valid and determinate assay result for the 1-month post-Vaccination 1 visit;
- Have no major protocol violation as determined by the study clinician.

Major protocol violations will be determined by clinical review. A major protocol violation is a protocol violation that, in the opinion of the sponsor's study medical monitor, would materially affect assessment of immunogenicity, eg, subject receipt of a prohibited vaccine or medication that might affect immune response or a medication error with suspected decrease in potency of the vaccine. The sponsor's medical monitor will identify those subjects with protocol violations before any immunogenicity analysis is carried out.

The evaluable immunogenicity population will be the primary analysis population for the immunogenicity endpoints evaluated among this cohort. Subjects will be included in the vaccine group as randomized in the analysis, which, by the population definition, is equivalent to the vaccine group corresponding to the vaccine received.

The evaluable immunogenicity population will also be the primary analysis population for the cellular assay results reported from this cohort.

4.1.3. Modified Intent-to-Treat Population

All randomized subjects who have at least 1 valid and determinate assay result related to the proposed analysis during Stage 1 will be included in the modified-intent-to-treat (mITT) population. Immunogenicity results based on the mITT population will be summarized according to the vaccination as randomized.

Analysis of immunogenicity results based on the mITT population will be considered supportive and will be performed for critical endpoints, such as secondary endpoints, only if there is enough difference (eg, >10%) between the evaluable immunogenicity population and the mITT population.

4.2. Primary Study Cohort - Stage 2

4.2.1. Safety Population

All subjects who were invited for Stage 2 and received at least 1 dose of the investigational products (RSVpreF or placebo) at Vaccination 2 (Visit 5) will be included in the safety population for this cohort. For the safety analyses, subjects will be analyzed according to the investigational product received. The safety population will be the only analysis population for Stage 2 safety evaluation.

4.2.2. Evaluable Immunogenicity Population

This evaluable immunogenicity population will include subjects who:

- Are eligible (have signed informed consent and met all inclusion/not met any exclusion criteria) and were randomized into the study;
- Have received vaccines (concomitant with SIIV) at Vaccination 1 and Vaccination 2 as randomized;
- Have a Visit 6 (1 month after Vaccination 2) blood draw for assay testing within 27 to 42 days after Visit 5, inclusive (after vaccine administration) (note: the 27- to 42-day interval is calculated as the Visit 6 date minus the Visit 5 date);
- Have at least 1 valid and determinate assay result for the 1-month post-Vaccination 2 visit;
- Have no major protocol violation as determined by the study clinician.

CCI

PFIZER CONFIDENTIAL

Major protocol violations will be determined similar to the description in [Section 4.1.2](#) by clinical review.

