In this study in older adults 65 to 85 years of age, a CpG with aluminum hydroxide (CpG/Al(OH)₃)-adjuvanted formulation, given as a single dose or in a 2-dose regimen administered 2 months apart, will be investigated to assess if the addition of CpG could further improve neutralizing antibody levels relative to formulations with or without Al(OH)₃ at the same dose levels used in the FIH study. In this event, a CpG/Al(OH)₃-adjuvanted formulation would be included in further development studies. CpG is a Toll-like receptor 9 (TLR9) agonist that has been generally well tolerated in human clinical trials for infectious disease indications, such as hepatitis B, malaria, and influenza.⁹ A CpG-containing hepatitis B vaccine, Heplisav-B, was recently licensed in the United States.¹⁰ CCI

Additionally, it is anticipated that an RSV vaccine would optimally be given at the same time as a seasonal influenza vaccine, to facilitate its use in the older adult population. Therefore, this study will assess any potential impact on safety, tolerability, and immune responses to the seasonal inactivated influenza vaccine (SIIV) when the RSV vaccine and SIIV are given concomitantly; similar assessments of concomitant administration of influenza vaccine and RSV vaccine with or without Al(OH)₃ are being conducted in the C3671001 study.

Data from the C3671001 study at 1 month after administration of the 3 dose levels of RSV vaccine (60 µg, 120 µg, and 240 µg), with or without Al(OH)₃ in subjects aged 18 to 85 years, have shown the vaccine is well tolerated and immunogenic, with a trend toward greater immunogenicity at the 240-µg dose level.

The C3671002 study was initiated under protocol Amendment 2 during the southern hemisphere influenza season; however, a delay in SIIV availability prevented the completion of enrollment of the original cohort. Consequently, only 250 subjects of the planned 312 subjects were enrolled. In Amendment 3, this cohort will be referred to as the Primary Study Cohort - Stage 1.

Protocol Amendment 3 will address 2 broad goals:

1. Evaluate a 2-dose regimen administered 2 months apart to determine whether a short dosing interval elicits an enhanced immune response.

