4.3. Criteria for Temporarily Delaying Vaccine Administration

The following conditions are temporary or self-limiting and a subject may be vaccinated once the condition(s) has/have resolved and no other exclusion criteria are met.

- Current febrile illness (oral temperature $\geq 100.4^{\circ}\text{F}$ [$\geq 38^{\circ}\text{C}$]) or other acute illness within 48 hours before investigational product administration.
- Any acute respiratory illness within 14 days before investigational product administration.

- Receipt of any inactivated vaccine within 14 days or any live vaccine within 28 days before or anticipated receipt of any vaccine within the 14 days after investigational product administration.
- Receipt of short-term (<14 days) systemic corticosteroids. Investigational product administration should be delayed until systemic corticosteroid use has been discontinued for at least 28 days. Inhaled/nebulized, intra-articular, intrabursal, or topical (epidural, skin, or eyes) corticosteroids are permitted.

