9.2.1. Immunogenicity Analysis Populations

For the immunogenicity analyses, 2 analysis populations will be defined for each study cohort: Primary Study Cohort - Stage 1, Primary Study Cohort - Stage 2, and the RSV Vaccine Month-0, Month-2 Cohort.

9.2.1.1. Primary Study Cohort - Stage 1

- **Evaluable immunogenicity population:** In general, the subject must have been eligible for the study, have received both SIIV and RSV vaccinations or SIIV and placebo to which he or she was randomized, have had blood drawn within the prespecified time frames at the 1-month postvaccination follow-up visit, have at least 1 valid and determinate assay result for the proposed analysis, and have no other major protocol violations.
- **Modified intent-to-treat (mITT) population:** A subject must have been randomized and have at least 1 valid and determinate assay result related to the proposed analysis.

9.2.1.2. Primary Study Cohort - Stage 2

- **Evaluable immunogenicity population:** In general, the subject must have been eligible for the study, have received vaccination and revaccination (concomitant with SIIV) to which the subject was randomized, have had blood drawn within the prespecified time frames at the 1-month post-Vaccination 2 follow-up visit, have at least 1 valid and determinate assay result for the proposed analysis, and have no other major protocol violations.
- **mITT population:** A subject must have been randomized in Stage 1, consented to participate in Stage 2 and have at least 1 valid and determinate assay result related to the proposed analysis.

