2.2. Study Design

This is a Phase 1/2, multicenter, randomized, placebo-controlled, observer-blind, dose- and formulation-finding study.

The study will evaluate the safety, tolerability, and immunogenicity of up to 7 different RSV vaccine candidates with bivalent formulations (RSV A and RSV B) at 3 dose levels of 60 µg of the prefusion RSV F antigens CCI [REDACTED] 120 µg CCI [REDACTED] and 240 µg CCI [REDACTED] formulated with aluminum hydroxide (Al[OH]₃) or CpG/Al(OH)₃, or a 240-µg RSV vaccine CCI [REDACTED] alone, when administered concomitantly with SIIV, or 240 µg formulated with CpG/Al(OH)₃ on a Month-0 and Month-2 schedule without SIIV.

The study is organized in the following cohorts:

1. The Primary Study Cohort - Stage 1 will evaluate 7 RSV vaccine doses/formulations given concomitantly with SIIV at Month 0.
2. The Primary Study Cohort - Stage 2 will evaluate revaccination of the Stage 1 subjects with the RSV vaccine and concomitant SIIV, administered at Month 12.
3. The RSV Vaccine Month-0, Month-2 Cohort will evaluate a 240-µg dose of the RSV vaccine with CpG/Al(OH)₃ given at Months 0 and 2. No concomitant SIIV will be given.

Male and female subjects 65 to 85 years of age will be enrolled. Subjects will be randomized equally across all dose groups in the primary cohorts. The RSV Vaccine Month-0, Month-2 Cohort will be randomized 1:1 to receive RSV vaccine or placebo.

Primary Study Cohort - Stage 1. Enrollment in the Primary Study Cohort - Stage 1 commenced in April 2019 and completed in June 2019. Approximately 250 subjects 65 to 85 years of age were equally randomized at Visit 1 to receive one of the 7 RSV vaccine doses/formulations or placebo (a total of 8 parallel groups), concomitantly with SIIV.

Primary Study Cohort - Stage 2. Prior to completion of Stage 1, subjects may be invited to participate in Stage 2. Safety and immunogenicity data obtained from the C3671001 and C3671002 studies will be used to determine whether Stage 2 will proceed and, if so, whether all or some of the RSV formulations will be evaluated.

Two protocol administrative change letters (PACLs) were distributed to the sites regarding initiation of Stage 2 vaccination. The first PACL, dated in January 2020, was to instruct the sites that all subjects would be revaccinated in Stage 2. The second PACL, dated in March 2020, was to instruct sites to postpone the initiation of Stage 2 until further notice because of the coronavirus disease 2019 (COVID-19) pandemic.

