4.3.2. Evaluable Immunogenicity Population

This evaluable immunogenicity population will include subjects who:

- Are eligible (have signed informed consent and met all inclusion/not met any exclusion criteria) and were randomized into the study;
- Have received both vaccinations at Months 0 and 2 as randomized;
- Have a Visit 4 (1 month after Vaccination 2) blood draw for assay testing within 27 to 42 days after Visit 3, inclusive (after vaccine administration) (note: the 27- to 42-day interval is calculated as the Visit 4 date minus the Visit 3 date);
- Have at least 1 valid and determinate assay result for the proposed analysis;
- Have no major protocol violation as determined by the study clinician.

Major protocol violations will be determined as described in [Section 4.1.2](#) by clinical review.

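### Stage 2's evaluable immunogenicity population sets no limit on the days between doses, and the Month-0, Month-2 population sets only a nominal one

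*SAP*

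**What the plan says.** For Stage 2, SAP 4.2.2 requires that subjects "Have received vaccines (concomitant with SIIV) at Vaccination 1 and Vaccination 2 as randomized". Its one numeric limit concerns sampling: "blood draw for assay testing within 27 to 42 days after Visit 5, inclusive". For the other two-dose cohort, SAP 4.3.2 requires that subjects "Have received both vaccinations at Months 0 and 2 as randomized", again with one numeric limit: "blood draw for assay testing within 27 to 42 days after Visit 3, inclusive".

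The protocol definitions add no interval. For Stage 2, Protocol 9.2.1.2 asks that subjects "have received vaccination and revaccination (concomitant with SIIV) to which the subject was randomized"; Protocol 9.2.1.3 is similar for the Month-0, Month-2 Cohort. The dose windows appear in the visit schedules and procedures: 300-400 days after Visit 1 for the Stage 2 dose (Protocol Table 2 and 6.2.1) and 54-66 days for the Month-2 dose (Protocol Table 3 and 6.3.4). No analysis set cites them.

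SAP 2.2 also reports a disruption: "The second PACL, dated in March 2020, was to instruct sites to postpone the initiation of Stage 2 until further notice", because of the pandemic. The SAP version containing that sentence is dated 9 June 2020 and adds no rule on dose interval.

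**The concern.** The dose interval is the subject of both cohorts. The Month-0, Month-2 Cohort was added to "Evaluate a 2-dose regimen administered 2 months apart to determine whether a short dosing interval elicits an enhanced immune response"; Stage 2 was added to learn whether a dose 12 months after the first supports annual vaccination (Protocol 1.2). SAP 7.2 says the interim results will inform the choice of dosing schedule.

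The planned summaries can be sensitive to that interval. SAP 3.2.1 derives fold rises from before dose 2, and from one month after dose 1 to one month after dose 2. A longer gap leaves more time for titers to wane before dose 2 and may change the boost after it. If subjects with materially different intervals are pooled under one label, the post-dose-2 GMTs and GMFRs do not describe the schedule that the label names.

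**Working it through.** The plan states no figure for this point, so there is none to reproduce, and no sample-size calculation is involved. The check is a reading of the criteria followed by date arithmetic.

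**1. Does any criterion bound the interval?**

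| Criterion | Stage 2 (SAP 4.2.2) | Month-0, Month-2 (SAP 4.3.2) |
|---|---|---|
| Doses received | Both, as randomized; no timing | Both, at nominal months; no days |
| Days from dose 2 to blood draw | 27-42 | 27-42 |
| Days from dose 1 to dose 2 | None | None |
| Protocol dose window, not cited | 300-400 | 54-66 |

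Within each cohort, randomization was to product, dose and formulation (Protocol 3.1, Table 4), so receipt as randomized carries no timing.

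**2. Does another provision close the gap?**

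- SAP 4.1.2 lets the medical monitor exclude major violations. Its examples are a prohibited vaccine or medication and a medication error that reduces potency. Dose timing is not named and no threshold is given.
- SAP 6.2.1.2 sets visit windows aside for blood sampling visits once a subject is evaluable.
- SAP 6.5.2 may tabulate blood-draw timing, but no dose-interval table is planned.
- SAP 4.2.3 and 4.3.3 run the mITT analysis only on request.

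**3. Stage 2 dates.** Inputs: Stage 1 enrolment April to June 2019 (SAP 2.2), with dosing at Visit 1; window upper limit 400 days (Protocol Table 2); SAP date 9 June 2020 (SAP Section 1). The documents give months only, so 1 April and 30 June are assumed as the outer dates.

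- Earliest limit: 1 April 2019 + 400 days = 5 May 2020.
- Latest limit: 30 June 2019 + 400 days = 3 August 2020.
- Days since Vaccination 1 on the SAP date: 435 for 1 April, 345 for 30 June.
- Cut-off: 9 June 2020 - 400 days = 6 May 2019. A subject vaccinated on 6 May is at exactly day 400, still inside the window; those vaccinated before 6 May are past it.
- Range for the assumption: with a first vaccination as late as 30 April 2019, day 400 is 3 June 2020 and the SAP date is day 406. Any April start therefore puts at least the first subject past the window by the SAP date.

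For illustration only, if revaccination took place in April-June 2021 (an assumption), the interval would run from 641 days (30 June 2019 to 1 April 2021) to 821 days (1 April 2019 to 30 June 2021). Such subjects would still meet every numeric criterion in SAP 4.2.2.

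**4. Month-0, Month-2 delays.** Protocol 4.3 delays vaccination for an acute respiratory illness in the preceding 14 days. An illness last present on day 60 moves dose 2 to about day 60 + 14 = 74, which is 74 - 66 = 8 days past the window. More generally, for a subject not yet given dose 2, an illness last present after day 66 - 14 = 52 pushes it past day 66. No prohibited medication is involved. A stopping-rule pause, which halts RSV vaccination (Protocol 7.4), could do the same.

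**The case against.** A reader might infer that neither population says anything about timing. That goes too far. SAP 4.3.2 names Months 0 and 2, and Protocol Table 3 maps Month 2 to 54-66 days, so a reasonable reader could import that window. SAP 4.2.2 refers to Visit 5, which Protocol Table 2 places at Month 12, days 300-400. This largely answers the Month-0, Month-2 half, where a cross-reference would do. It answers the Stage 2 half less well: the visit is named, but the criterion does not require it to have occurred in its window.

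The corticosteroid rule is a tempting illustration of a long delay: "Investigational product administration should be delayed until systemic corticosteroid use has been discontinued for at least 28 days". It is a poor one. Protocol 5.8.2 prohibits immunosuppressive therapy on study apart from listed local routes, and a prohibited medication is among the SAP's own examples of a major violation. That subject might be excluded whatever the interval.

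The major-violation route is broader than its examples, which are not exhaustive, and it must be applied before any immunogenicity analysis. A dose after day 400 departs from the Visit 5 window and could be caught. This stands, so inclusion of a late dose is the default and not a certainty. But the decision would be case by case, without a stated threshold, on the variable under study.

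The impact is also limited. Both cohorts are exploratory, and no planned GMR compares the 2-month and 12-month schedules. The Stage 2 HAI ratios compare arms within the same stage, so a general delay would affect all arms. The neutralizing-titer ratios in SAP 6.2.1.2 use post-Vaccination 1 data only. All of this stands and confines the point to the descriptive post-Vaccination 2 summaries.

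**Conclusion.** The gap is real and worth closing. It is clear for Stage 2: the evaluable definition has no dose-interval limit, and the SAP was issued while Stage 2 was on hold and, on any April 2019 start, after the first subjects had passed day 400. Followed as written, it would count late second doses as Month-12 revaccination unless the medical monitor intervened. For the Month-0, Month-2 Cohort it is a weaker gap, a nominal month without a cited window.

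The documents do not show that any late dose was given, and without an enrolment distribution the number of affected subjects cannot be derived. Nor do they support a simple rule that drops every Stage 2 subject outside 300-400 days: if dosing resumed after about 3 August 2020, that would empty the evaluable set, and the mITT analysis is not a dependable fallback. The primary safety endpoints are unaffected. The dates rest on the assumed enrolment limits of 1 April and 30 June 2019.

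**What to change.** - **SAP 4.3.2:** tie Months 0 and 2 to the protocol's 54-66 day window for the evaluable set.
- **SAP 4.2.2:** state how a Vaccination 2 outside 300-400 days is classified, reconciled with the protocol window. Settle this before unblinding and database release, the point by which SAP Section 4 already requires subjects to be classified.
- **Both cohorts:** tabulate the actual interval from Vaccination 1 to Vaccination 2 (median and range) by arm, and show post-Vaccination 2 GMTs and GMFRs separately for in-window and out-of-window subjects.
- **If Stage 2 resumes after the window:** label its results by the actual interval and do not report them as evidence on 12-month revaccination.

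The cost is SAP wording, one interval table and a split display. The in-window sets would be smaller, and the Stage 2 one might be empty. The separate display keeps the late-dosed subjects visible, which matters because the mITT analysis is run only on request. None of this alters when anyone is vaccinated.
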